**INSTRUCTIONS:**

- Use “*TEMPLATE PROTOCOL (HRP-503)*” to prepare a document with the information from following sections.
- Depending on the nature of your study, some sections may not be applicable to your research. If so mark as “NA”. For example, research involving a retrospective chart review may have many sections with “NA.” For subsections, like 1.x or 8.x, you can delete it if it’s not applicable.
- When you write a protocol, keep an electronic copy. You will need to modify this copy when making changes.
- As you are writing the protocol, remove all instructions in italics so that they are not contained in the final version of your protocol.
- Omit starred (\*) items if this is the activation of a protocol at a new site or sites that will be overseen by a principal investigator who will take separate and full responsibility for that site or those sites. Complete by describing information specific to the site(s). Do not repeat information in the approved protocol that applies to all site(s).

**REVISION HISTORY**

Revision #	Version Date	Summary of Changes	Consent Change?
1	4/19/2022	Added self-report and interview measures, more detailed exclusion criteria. Added protocol for assessing and addressing risk for suicide, and training for basic life support.	Yes
2	6/24/2022	Updated locations in which recruitment flyers can be posted and distributed. Additional self-report survey (DASS-21). Changes are highlighted in red.	No
3	8/12/22	Updated recruitment location to include ResearchMatch	No

PROTOCOL TITLE:

4	6/28/2024	Added recruitment site	No

## 1.0 Study Summary

Study Title	Studying Reward Processing with fMRI, EEG, and TMS
Study Design	Within-subject Experimental/Control Design
Primary Objective	The purpose of the proposed research is to examine the impact of TMS on brain activity that has been linked to anhedonia using functional magnetic resonance imaging (fMRI) and EEG.
Secondary Objective(s)	
Research Intervention(s)/Investigational Agent(s)	NA
IND/IDE #	
Study Population	Adults, aged 18-55
Sample Size	80
Study Duration for individual participants	10-15 hours over 4-5 weeks
Study Specific Abbreviations/Definitions	fMRI – functional magnetic resonance imaging EEG – Electroencephalogram TMS – transcranial magnetic stimulation

## 2.0 Objectives\*

### 2.1 *Describe the purpose, specific aims, or objectives.*

The purpose of the proposed research is to further our understanding of neural activity that has been linked to anhedonia (i.e., reward-related neural activity) – by examining the impact of multiple TMS sessions on reward-related neural activity. Our goal is to assess whether stimulating medial prefrontal cortex, relative to the inion, produces increases in neural response to rewards using EEG and fMRI. EEG, fMRI, and TMS are well-established, non-invasive techniques used by thousands of labs around the world to study brain function—and this work would begin to suggest specific ways to modulate neural activity that has been implicated in anhedonia and depression.

### 2.2 *State the hypotheses to be tested.*

We hypothesize that stimulating the medial prefrontal cortex (MPFC), relative to a control site (i.e., inion), using TMS (i.e., 5 sessions over a week) will result in increases in reward-related EEG and fMRI measures. We additionally examine whether TMS will result in changes in self-report measures.

### 3.2 *Describe any relevant preliminary data.*

We recently found that a single session of TMS to MPFC increased the RewP; that paper is currently under review and forms the basis for the current paper. We are interested in whether a more protracted TMS protocol to MPFC (5 sessions within a week) would increase reward-related neural measures relative to a control site – and if those changes might be longer lasting and relate to changes in self-report.

### 3.3 *Provide the scientific or scholarly background for, rationale for, and significance of the research based on the existing literature and how will it add to existing knowledge.*

We and others have found in multiple studies that depression is associated with reduced reward-related neural activity measured with fMRI and EEG. Both are non-invasive tools that researchers have for studying human brain function, especially in the context of depression. Yet, there have been no causal demonstrations that increasing reward-related neural activity results in changes in depression or related experiences. Here, we focus on anhedonia—the degree to which individuals report day-to-day activities as enjoyable—as individual differences in anhedonia have consistently been linked to reward dysfunction.

## 4.0 Study Endpoints\*

4.1 *Describe the primary and secondary study endpoints.*

NA

4.2 *Describe any primary or secondary safety endpoints.*

NA

## 5.0 Study Intervention/Investigational Agent

1.1 *Description: Describe the study intervention and/or investigational agent (e.g., drug, device) that is being evaluated.*

NA

5.1 *Drug/Device Handling: If the research involves drugs or device, describe your plans to store, handle, and administer those drugs or devices so that they will be used only on subjects and be used only by authorized investigators.*

NA

5.2 *If the drug is investigational (has an IND) or the device has an IDE or a claim of abbreviated IDE (non-significant risk device), include the following information:*

NA

## 6.0 Procedures Involved\*

6.1 *Describe and explain the study design.*

In the proposed research, we will use computer-based tasks that examine reward processing. Subjects will be screened by the MR technologist, and will be excluded if they meet any exclusion criteria. Subjects will be given instructions about the task and the MRI scanning environment. If there is any concern about claustrophobia, participants will be encouraged to try the mock scanner before entering the MRI scanner. The mock scanner is located next door to the MRI scanner and provides a simulated MRI

environment. If they are uncomfortable with the enclosed environment (at any time), they can exit the study and receive compensation for their time. Otherwise, participants will then be given a short practice session on the task either before entering the scanner, or during collection of preliminary and/or structural images. After being positioned in the scanner by the technologist, the technologist will acquire initial calibration scans. A structural image of the head and brain may be acquired before or after the functional imaging data. The remaining time in the scanner will be used to collect functional imaging data while subjects perform the task. Response time and accuracy data will be recorded during the task. We will relate these measures to the fMRI data from the scanner, in order to understand the relationships between neural activity and behavioral performance.

All TMS studies will conform to the safety limits established by Rossi et al., 2009 and recently updated by Rossi et al., 2021. Two types of offline designs may be used: A) Continuous Theta-Burst stimulation (TBS), which is one of the most widely used offline techniques in which 600 pulses are delivered in bursts of 3 pulses (at 50 Hz) repeated at a rate of 5 Hz. This technique was introduced in 2005 by Huang et al. and has been used in hundreds of studies since. B) Intermittent TBS, which is another widely used offline technique introduced by Huang et al., 2005. As in continuous theta burst stimulation, 600 pulses are delivered in 50 Hz bursts every 5 Hz. However, in intermittent TBS, 2 seconds of stimulation is alternated with 8 seconds of no stimulation. Hence, the entire set of pulses is delivered over 190 seconds. Again, all procedures will conform to safety limits established by Rossi et al. 2009 and updated by Rossi et al., 2021. The versions of TBS that we administer have especially low rates of adverse effects (Oberman et al., 2011; Rossi et al., 2021).

In order to dose appropriately the TMS stimulation, it is necessary to determine an individual's sensitivity to TMS. This is done by delivering TMS to the motor cortex to affect muscle activity in the hand in order to record the motor threshold (MT). MT is the standard in the field for determining the intensity of TMS for each individual to ensure participant safety. MT will be determined in one of two ways: 1) Recording electromyography (EMG) of the first dorsal interosseus muscle of the hand contralateral to TMS to monitor muscle activity. In this case, persistent muscle activity will be elicited by having the participant activate the muscle using the appropriate flexion movement, and the effect of TMS on the muscle will be observed as a brief cessation of EMG activity. This is referred to as the active motor threshold (AMT). 2) Observing a visually-identified hand twitch in the hand contralateral to TMS (e.g.

if applying TMS to the left hemisphere of the brain, a twitch will be observed in the right hand). This is referred to as the resting motor threshold (RMT). In both cases, the scalp region producing the largest hand twitch will be identified. To identify this region, TMS will be set to 30% of the maximal stimulator output, which is well below the motor threshold for most, if not all, individuals. TMS will be delivered to a scalp location approximating the location of motor cortex based upon surface features using the nose and ears as landmarks. From this initial location, TMS will be delivered. If ineffective to produce a hand twitch, the TMS coil will be moved to a new, nearby site, which will subsequently be tested. This process will continue until a grid of locations has been tested around the starting location, approximating 5 cm^2. If a hand twitch has not been produced, this indicates that the stimulation is below threshold and the stimulator output will be raised by 5% of the maximum stimulator output. The process will then repeat until the maximal hand twitch at a given stimulation level is observed, thereby indicating the location of interest. During this process, the participant will be closely monitored and periodically asked whether the stimulation is producing any discomfort or unusual symptoms (e.g. dizziness). At the scalp location of interest, the lowest TMS intensity able to elicit 5 visible cessations of EMG activity in 10 trials (AMT), or 5 visible twitches in 10 trials (RMT) at this site will be determined. Individual MT will be used to determine the intensity of stimulation for each individual, as recommended by safety guidelines. This procedure usually takes about 5 minutes and also serves the purpose of acquainting participants to TMS stimulation. Once MT is determined, TMS will be administered within the limits of the safety guidelines recently updated in Rossi et al., 2021. An additional 12 years of research using TBS ranging between 80% and 100% RMT was examined to determine the continued efficacy of previously established guidelines in Rossi et al., 2009. Since the 2009 publication, the scientific community has gained a better understanding of safety risks and the rarity of adverse events (such as seizure) associated with TMS. To reflect current safety guidelines for offline studies using TBS, TMS will never exceed 100% of RMT or 120% of AMT.

TMS will be delivered to multiple sites of interest. Site order will be randomized across participants.

Electroencephalography (EEG) will be used to measure changes in brain activity caused by TMS. The EEG assesses electrical brain activity through surface recording disks (electrodes) which are placed near the participant's head. The electrodes transmit the signals, which are then amplified (via an 8 channel Brain Vision

LiveAmp) and stored on a computer. The procedure is entirely non-invasive.

An electrode cap will be placed on the participant's head. In order to record brain activity, these disks need to be filled with a gel which allows the electrodes to better record brain activity at the scalp. Therefore, the participants in this study will need to clean their hair after participation. The gel is completely water soluble, and the procedure is painless. The MRI facility has sinks and towels, and the investigators will help to make sure the participant has thoroughly rinsed all the gel from their hair. After an accurate signal is assured, the signal derived from the electrode cap is then amplified, transmitted to a computer, and stored for later analysis. In addition to the EEG recording, muscle activity from around the eyes may be recorded from the subjects. Muscle activity from around the eyes is recorded by two small sensors that will be placed below the participant's left eye, as well as behind the ears. These procedures are completely noninvasive and painless.

*6.2 Provide a description of all research procedures being performed and when they are performed, including procedures being performed to monitor subjects for safety or minimize risks.*

Below is a description of the kinds of tasks that participants will perform. In general, tasks will range in duration from 5-10 minutes to 1-2 hours. Breaks will be given every 5-10 minutes. Multiple sessions may be performed. Based upon performance on the tasks, we may contact participants to perform other related tasks. Returning to perform other tasks will be optional and have no bearing upon the tasks the participants have already completed.

- Computer-based Tasks
  - Doors Task
    - a. Participants will be shown graphics depicting doors, and will be asked to choose a door. After picking a door, participants receive feedback on the screen indicating whether they have won or lost on that trial. The participants' goal is to do their best to win as much money as possible. In this task, participants will receive a monetary bonus for correct guesses, which will total between \$0.00 and \$10.00 depending on how many correct guesses they make. This task will take approximately 5-10 minutes.
  - Motivated Behavior Task

- a. Participants will be given the opportunity to complete a specified number of trials for a specified reward. Trials will entail trials of the tasks described above or other simple cognitive tasks such as arithmetic.
- Written tasks
  - DARS
    - a. Self-reported anhedonia will be measured using the Dimensional Anhedonia Rating Scale (DARS). The DARS is an appealing measure due to its high internal consistency, convergent validity with other measures of anhedonia, divergent validity with depression scores, and ability to capture state levels of anhedonia. This latter property makes it suitable for measuring changes in anhedonia.
  - Screening
    - a. Participants will be screened to be fluent in English, between the ages of 18-55, and to have no contraindications for MRI or TMS. Participants will also be screened such that they do not belong to populations vulnerable to the Coronavirus Disease (COVID-19), and have not been exposed. To be eligible for participation in this study, participants must score 46 or below on the DARS, reflecting increased anhedonia.
  - Demographics
    - a. Demographic information including age, gender, race, and ethnicity will be collected. This information will be used for reporting purposes to demonstrate fair inclusion. Participants will be informed that providing this information will be optional. This information has no direct bearing upon the research to be performed
  - Handedness
    - a. Edinburgh Handedness Inventory, which asks about which hand is used in various tasks, will be collected to determine the dominant hand.

- DSM Crosscutting
  - a. The DSM-5 Level 1 Cross-Cutting Symptom Measure is a self- or informant-rated measure that assesses mental health domains that are important across psychiatric diagnoses.
- World Health Organization Disability Assessment Schedule (WHODAS)
  - a. The WHODAS is a generic assessment instrument developed by WHO to provide a standardized method for measuring health and disabilities across cultures.
- Patient Health Questionnaire (PHQ-9)
  - a. The PHQ-9 is a brief depression severity measure.
- Generalized Anxiety Disorder (GAD-7)
  - a. The GAD-7 is a brief measure for assessing generalized anxiety disorder.
- Quick Inventory of Depressive Symptomatology (QIDS-SR)
  - a. The QIDS-SR is a brief self-report assessment of depressive symptoms.
- Pain scale
  - a. Self-reported pain scale.
- Depression Anxiety and Stress Scale (DASS 21)
  - a. a 21-item questionnaire to assess symptoms of depression, anxiety and stress.

  

- Interviews
  - Montgomery-Asperg Depression Rating Scale (MADRS)
    - a. The MADRS is a diagnostic questionnaire to measure the severity of depressive episodes.

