Transient cognitive/neuropsychological changes. Some repetitive TMS protocols have been shown to affect cognitive processing for up to one hour following stimulation. Specifically, this is the case for "offline" techniques such as 1 Hz stimulation and theta-burst stimulation (TBS; Huang et al., 2005). These changes are small, but could in theory affect the subject's ability to drive home safely. However, our use of offline TMS always precedes the actual experimental task that subjects are performing. Since the effects of the TMS parameters we are proposing to use have never been observed to last more than 1 hour, the potential cognitive effects of TMS are

expected to have worn off by the time the testing session is concluded. Participants may experience frustration from poor performance on the task. Another potential risk is probing for personal or sensitive information in surveys, interviews, or questionnaire.

Although we do not expect it to occur frequently, some subjects may endorse suicidality or increased risk for suicidality; in this event, we will implement the following protocol:

Participants will have a clinical interview performed, and as part of that clinical interview, we will assess suicidality. If participants endorse any suicidal ideation, the severity of suicidality will be assessed using the structured interview on the following pages, and the Joiner method. This procedure is adopted from the FSU Psychology Clinic using the clinic's suicide decision tree, which is an empirically validated structured interview.

Joiner et al. (1999) use the following method to designate risk severity:

1. An individual's risk for suicide is designated nonexistent if he or she has no current suicidal symptoms, no history of suicide, and no or few other risk factors.
2. Risk for suicide is considered mild if the individual is a multiple attempter with no other risk factors or is a non-multiple attempter experiencing suicidal ideation of limited intensity and duration, no or mild Resolved Plans and Preparation, and no or few other risk factors.
3. An individual is designated at moderate risk if he or she is a multiple attempter with any other significant risk factor. A non-multiple attempter with moderate to severe Resolved Plans and Preparations or moderate to severe Suicidal Desire and Ideation accompanied by at least two other risk factors is also considered to be at moderate risk for suicide.

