## 17.0 Data Management\* and Confidentiality

17.1 *Describe the data analysis plan, including any statistical procedures or power analysis.*

Data analysis will follow standard procedures detailed in the relevant literature including frequentist tests and Bayesian statistics when applicable. Power analyses will be performed on relevant past and/or preliminary data to inform planned sample sizes. If such data are not available, power analyses will be performed based on anticipated effect sizes.

17.2 *Describe the steps that will be taken to secure the data (e.g., training, authorization of access, password protection, encryption, physical controls, certificates of confidentiality, and separation of identifiers and data) during storage, use, and transmission.*

The steps that will be taken to secure the data (e.g., training, authorization of access, password protection, encryption, physical controls, certificates of confidentiality, and separation of identifiers and data) during storage, use, and transmission include retaining information in digital format. Digital information will be stored on password protected local machines, or on secure cloud based services such as Google Docs also requiring a password.

17.3 *Describe any procedures that will be used for quality control of collected data.*

PROTOCOL TITLE:

NA

*17.4 Describe how data or specimens will be handled study-wide:*

- *What information will be included in that data or associated with the specimens?*
- *Where and how data or specimens will be stored?*
- *How long the data or specimens will be stored?*
- *Who will have access to the data or specimens?*
- *Who is responsible for receipt or transmission of the data or specimens?*
- *How data or specimens will be transported?*

NA

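### The plan does not provide for EEG and fMRI data to be processed without knowledge of stimulation site, and fixes no processing or exclusion rules for its directional within-person contrast

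*Combined protocol and SAP*

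**What the plan says.** Section 1.0 describes a "Within-subject Experimental/Control Design". Sections 2.1 and 2.2 set MPFC against the inion as control site, with five TMS sessions over a week, and predict a direction: stimulation "will result in increases in reward-related EEG and fMRI measures". Section 2.2 then adds: "We additionally examine whether TMS will result in changes in self-report measures". Sections 3.1 and 3.2 report the team's own earlier single-session result in the same direction as the basis for this work.

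On allocation, 6.1 says "Site order will be randomized across participants". On EEG handling, it says the amplified signal is "transmitted to a computer, and stored for later analysis". On analysis, 17.1 says "Data analysis will follow standard procedures detailed in the relevant literature" and mentions frequentist and Bayesian methods in general terms. Endpoints (4.1) and quality control of collected data (17.3) are both answered NA.

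The MADRS is named once, under Interviews in 6.2: "The MADRS is a diagnostic questionnaire to measure the severity of depressive episodes". No timing, rater or endpoint status is given. Section 15.1 separately says "Participants will have a clinical interview performed, and as part of that clinical interview, we will assess suicidality", also without saying when this falls relative to stimulation.

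No masking of participants, TMS operators, interviewers or data analysts appears in the text reviewed. The only masks mentioned are COVID-19 face coverings, and sham stimulation appears only in a side-effect rate from another study.

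**The concern.** Randomising site order guards against period effects. It does nothing about a person who knows which recording followed MPFC stimulation while deciding which epochs, runs or participants to keep. In a within-person design, any such decision that leans with site goes directly into the paired difference, and the predicted direction is known in advance.

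Other safeguards that might limit this are absent from the text. No endpoint is named, no EEG or fMRI processing rule is fixed, and no quality-control procedure is described. Section 14.1 also allows staff to withdraw people for inattention or for misunderstanding the task, which are matters of judgement. At stake is the credibility of the MPFC-versus-inion result. Once data have been processed with site visible, the doubt is hard to remove afterwards.

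**Working it through.** The plan has no figure of its own here. It gives no alpha, power, effect size or SD, and 17.1 defers power analysis. The check therefore has two parts.

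**Part 1: what the text fixes, step by step**

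| Step | What the document provides |
|---|---|
| Order of sites | Randomised (6.1) |
| Coding of site on stored files | Nothing stated |
| Who processes EEG/fMRI, and what they know | Nothing stated |
| Artefact rejection and exclusion rules | Nothing beyond standard procedures (17.1) |
| Quality control | NA (17.3) |
| Endpoint definition | NA (4.1) |
| MADRS timing, rater, comparison by site | Nothing stated (6.2) |

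From recording to test statistic, only the order of sites is protected.

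**Part 2: how sensitive a paired comparison is to a small shift (illustration only)**

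Inputs:
- n = 80 (sample size, 1.0) and n = 150 (local accrual, 12.1). The two sections differ, so both are shown. Each is taken as complete pairs, which is an assumption.
- Two-sided alpha 0.05 (assumed; not stated in the plan).
- True site effect zero (assumed).
- Processing shift b, in SDs of the within-person difference (assumed; no source in the documents).

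Formula: with F the noncentral t distribution function on n − 1 degrees of freedom and noncentrality b√n, and t* the 97.5% point of the central t,

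P(reject) = 1 − F(t*) + F(−t*).

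For n = 80, √80 = 8.944 and t* = 1.990. For n = 150, √150 = 12.247 and t* = 1.976.

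| b | b√80 | P(reject), n=80 | b√150 | P(reject), n=150 |
|---|---|---|---|---|
| 0 | 0 | 0.050 | 0 | 0.050 |
| 0.05 | 0.447 | 0.073 | 0.612 | 0.093 |
| 0.1 | 0.894 | 0.143 | 1.225 | 0.230 |
| 0.2 | 1.789 | 0.424 | 2.449 | 0.682 |

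Two things follow. A shift of 0.1 difference-SDs raises the error rate at n = 80 by a factor of 0.143/0.05 = 2.9. And enrolling more people does not dilute the bias: the noncentrality grows with √n, so every non-zero row is worse at 150 than at 80.

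The arithmetic is that of power for a paired t-test, with b read as bias instead of effect. It shows sensitivity and says nothing about how large b is in this trial.

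**The case against.** **The documents are silent, which is not evidence of unmasked practice.** This is correct. Nothing says who processes the data or what they know, so a reader who infers that the processors are aware of site goes further than the text. What stands is that the plan does not provide for masking.

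**The MADRS interviewer could create a site difference.** A reader might infer this from an interviewer-rated scale with no masked rater. The documents do not support it. The hypotheses in 2.2 name EEG, fMRI and self-report only. The MADRS appears once, with no timing and no comparison between sites. A screening or descriptive role fits equally well, since 10.2 excludes on psychiatric grounds and 15.1 describes a clinical interview. If the MADRS is given only before stimulation, it cannot produce a site difference.

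**A coding step would cost nothing and prevent the problem.** A reader might conclude this too, but it is too strong. File codes cannot mask a live interviewer. A separate rater is a staffing matter, and the trainee clinicians in 19.2 are mentioned only for contacting people at imminent risk. Coding also leaves participant expectation untouched, because the person being stimulated can tell where the coil is.

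**The larger gap is the unspecified analysis.** Much of this stands. Coded files without fixed rules would leave pipeline choices open once the key is known, so the remedy has to include both.

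**The percentages are not specific to this trial.** Agreed. Neither the size of b, nor its direction, nor the alpha level comes from the documents. The figures should not be read as the trial's expected false-positive rate.

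**Conclusion.** The point holds for EEG and fMRI processing. The text makes no provision for processing without knowledge of site and fixes no rules that would limit discretion, while the main contrast is directional and within-person. The size of any resulting bias cannot be obtained from the documents. Under the stated assumptions, a false-positive rate of 5% would become about 7%, 14% or 42% at n=80, and 9%, 23% or 68% at n=150, for shifts of 0.05, 0.1 and 0.2 difference-SDs.

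For the MADRS the conclusion is conditional. Its timing and role need to be stated, and rater masking matters only if it is given after stimulation and compared between sites.

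The change is worth making because it is cheap and has to be in place before processing starts.

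**What to change.** **In 17.1:**
1. Label EEG and fMRI files with a neutral block code, with the key held by a team member who does not process the data.
2. Write down the artefact-rejection, exclusion and preprocessing rules, and complete those steps before the site key is opened.
3. State that this reduces processing bias and does not blind participants or their self-report.

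**In 6.2:**
4. State whether the MADRS is given after stimulation and compared between sites. Only if so, and where existing staff allow, have it rated by someone who did not deliver that block's TMS and is not told the site, with participants asked not to reveal coil position.

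**Cost.** Items 1 to 3 need a file-coding step and the writing of rules that the analysis needs in any case. They need no extra staff and no change to stimulation, visits or sample size. Item 4 is one sentence if the MADRS is not a post-stimulation outcome; if it is, the cost is scheduling a second person. If none is free, items 1 to 3 still apply.
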